19.3 Population for Analyses

Full analysis set (FAS): The set of subjects determined according to the principle of Intention to Treat (ITT) refers to the data set composed by all subjects who are involved in the trial randomly and have used the trial product. The missing data were carried forward using the strategy of WCCF (Worst Case Care Forward) in case the primary efficacy endpoints of the patients were not observed. FAS is the primary analytical data set for evaluating validity.

Per protocol set (PPS): PPS is a subset of the FAS and includes subjects randomly assigned to treatment with a test or control device who have not experienced significant protocol deviations. The PPS is the secondary analytical data set for evaluating validity.

Safety analysis set (SS): This includes all subjects who have been formally enrolled and completed catheterization and dressing securement with the catheter in place for more than 24 hours. This data set is used to evaluate the safety of this trial.

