9.0 POINT OF ENROLLMENT AND EXIT

9.1 Point of Enrollment

Following recruitment and eligibility screening, a subject will sign the informed consent form. A subject is considered enrolled in this study at time the Informed Consent process has been completed.

Eligible and consented subjects will be assigned a unique subject identification number, which will not contain information that could identify the subject.

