9.2 Point of Exit

Study subjects may exit the study for a variety of reasons. The Investigator shall record the reason for withdrawal and discontinuation of the study in the applicable Case Report Form. These reasons include, but are not limited to:

- Study completion (all study related visit(s) are completed)
- Withdrawal by the Subject
- Withdrawal by Investigator
- Lost to follow-up
- Death
- Study Termination

If a subject withdraws or discontinues participation before study completion, the subject will not be accounted into the per protocol set (PPS) analysis until the required enrollment is reached but will be accounted into the safety set analysis.

[figure not shown]
Data collected until the last known contact of study subject may be used in the analysis of study data. Because the subjects in this study are all ICU patients, patients will be considered lost to follow-up if they are transferred out of the ICU or discharged without removal of the CVC. If the study subject withdraws from the study for any reason and there is an ongoing safety event, additional safety event information may need to be collected by the Investigator and shared with Sponsor.

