6.2.2 General Information

- (1) Evaluation Indicators
 - 1) Demographic information: Age, gender, nationality, height and weight;
 - 2) General Condition: medical history, allergic history.
 - 3) Deep vein indwelling catheterization and peripheral skin evaluation status: Insertion site, insertion type, duration of insertion (days), with or without blood oozing after puncture placement, whether other products were applied, whether emergency insertion was performed, whether skin assessment around the insertion site was performed, skin assessment around the insertion site (including erythema, edema, pruritus score and whether skin infection was diagnosed);
 - ♦ Methodology for calculating relevant indicators:
 - ✓ Age (years) = (date of informed consent date of birth + 1) / 365.25, rouding to whole numbers
 - ✓ Duration of tube insertion (days) = date of randomization date of tube insertion + 1
- (2) Evaluation method

FAS was used for evaluation.

The demographic data, general conditions were described accordingly to their numerical characteristics and quantitative indicators were compared between the two groups of participants using t-test/Wilcoxon rank sum test; qualitative indicators were compared between the two groups of participants using chi-square test/Fisher exact probability method.

Summary of the evaluation of deep vein indwelling catheterization and surrounding skin at the level of the insertion site. The two groups of quantitative indicators were compared using t-test/Wilcoxon rank sum test according to their corresponding numerical characteristics description; and the two groups of qualitative indicators were compared using chi-square test/Fisher exact probability method.

In addition, a list of data on medical history, allergic history, deep vein indwelling catheterization prior to enrollment and skin evaluation around the insertion site, and previous/concomitant medication was made for both groups of participants.

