6.3 Efficacy Evaluation

6.3.1 Primary Efficacy Evaluation

(1) Evaluation Indicators

Occurrence rate of bacterial colonization of the CVC tip segment and skin at the insertion site after extubation (number of culture-positive cases/total catheters × 100%)

Primary endpoint: Positive rates of catheter tip cultures and sampling cultures of skin surrouding the insertion site in patients with deep vein indwelling catheterization after CVC tubes were removed.

(2) Evaluation method

FAS and PPS were used for both total catheter count and participant level evaluation. If more than one catheter of the same type was available for the same participant and the culture results were inconsistent, a positive culture result was taken for that participant when participant-level analysis was performed.

Describe the number and percentage of cases of bacterial colonization of the CVC tip segment and skin at the insertion site after extubation in both groups, and compare the two groups using a chi-square test or Fisher's exact test.

In addition, because some subject may have two or more than two CVC, which are interrelated, a generalized mixed linear model was developed to evaluate the difference in the occurrence rate of bacterial colonization between the two groups, using the occurrence rate of bacterial colonization of the CVC tip segment after extubation and the occurrence rate of bacterial colonization of the skin at the CVC insertion site after extubation as dependent variables, group as a fixed effect, and insertion site, skin infection of baseline insertion site, and their interaction as random effects, respectively.

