6.4 Safety Evaluation

- (1) Evaluation Indicators
 - 1) Adverse events;
 - 2) Vital signs: including temperature, respiration, pulse, systolic blood pressure, diastolic blood pressure;
 - 3) Laboratory Check: Blood routine:
 - 4) Effects on the skin of the covered area, e.g. local infection, local skin irritation.
- (2) Evaluation method

Safety analysis was performed using the safety analysis population (SS).

The adverse event was coded according to the latest edition of the Medical Dictionary for Regulatory Activitie (MedDRA). Adverse events that occurred prior to randomization will be listed in the list only.

The analysis of AE will be based on Treatment Emergent Adverse Event (TEAE) during the treatment period. Any AE after the first application of the investigational device, whether or not related to the investigational device, will be defined as a TEAE, as will an AE that existed prior to the application of the investigational device but that worsens during the treatment period. In cases where AE cannot be defined as occurring before the first application of the investigational device or after the first application of the investigational device of the investigational device, AE will be classified as occurring after the first application of the investigational device as the most conservative approach.

The number of cases, case times, and percentages of all TEAEs, TEAEs belonging to CLABSI, TEAEs belonging to CRBSI, and TEAEs occurring in association with the investigational device are tabulated and summarized by system organ (SOC), preferred term (PT), and severity, respectively, for each group. Multiple occurrences of the same adverse event in the same participant will be summarized using the most severe one for severity and relevance to the investigational device.

TEAEs leading to study discontinuation, serious adverse events, and adverse events leading to death were summarized for each group by system organ (SOC), preferred term (PT), respectively, in descending order of the number of cases occurring in the test group.

Adverse events associated with the investigational device included a relationship to the investigational device determined to be: "relevant", "may be relevant".

Adverse events that led to study discontinuation included the choice of measures taken for the investigational device as: "Permanent deactivation of the investigational device".

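### The safety set's 24-hour catheter rule may leave treated subjects out of the safety tables, and it conflicts with Protocol 9.2 for early exits with a short catheter dwell

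*Protocol*

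**What the plan says.** Protocol 19.3 and SAP 5.3 define the safety set in the same terms: formally enrolled subjects who "completed catheterization and dressing securement with the catheter in place for more than 24 hours". No starting point and no particular catheter is named in either place.

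SAP 6.4 names the safety set as the population for its safety analysis. It also sets out the tables that depend on it: "TEAEs leading to study discontinuation, serious adverse events, and adverse events leading to death were summarized for each group", together with treatment-emergent events overall, device-related events and skin scores.

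Protocol 9.2 says of subjects who leave before completion that they are outside the per-protocol set "but will be accounted into the safety set analysis". It attaches no minimum time. The exit reasons in the same section are introduced by "The Investigator shall record the reason for withdrawal and discontinuation of the study in the applicable Case Report Form", and the list includes death.

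The full analysis set (Protocol 19.3, SAP 5.1) asks only for randomization and use of the product. In SAP 6.4 an event is treatment-emergent from the first application of the device, with no lag.

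**The concern.** A safety population normally contains everyone exposed. Here a subject can be randomized, receive a study dressing, have an event that meets the SAP's own definition of treatment-emergent, count in the full analysis set, and still be outside the safety tables because the catheter was in for 24 hours or less.

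Two things are at stake. First, the tabulated rates could leave out exposed subjects with short dwell, and some of these may have left early because something went wrong. Second, with no clock and no index catheter stated, and with Protocol 9.2 giving a different rule, two analysts could build different safety sets from the same database.

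**Working it through.** The plan gives no figure to reproduce, so the main check compares the rules.

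**1. Who is in which set.** Take a randomized subject with a study dressing applied and a catheter dwell of 24 hours or less.

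| Rule | Source | In or out |
|---|---|---|
| Full analysis set | Protocol 19.3, SAP 5.1 | In |
| Treatment-emergent event window | SAP 6.4 | Open from first application |
| Safety set definition | Protocol 19.3, SAP 5.3 | Out |
| Early-exit rule, if the subject withdrew or discontinued | Protocol 9.2 | In the safety set |
| Early-exit rule, if the catheter was removed and the study completed | Protocol 9.2 | Does not apply |

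The first two rows do not contradict the safety set rule; they show that the subject was exposed. The contradiction lies between the third and fourth rows, and only for early exits whose catheter dwell is 24 hours or less.

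**2. Which early exits are caught.**
- Withdrawal or discontinuation: caught only if the dwell is 24 hours or less. Leaving the study early does not mean that the catheter came out.
- Death: caught if the exit list in Protocol 9.2 is read as defining discontinuation. The list also contains study completion, so this is an inference.
- Loss to follow-up: not caught by itself. Protocol 9.2 defines it as leaving the ICU or hospital with the CVC still in.

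Protocol 9.2 is also too wide. Under Protocol 9.1, "A subject is considered enrolled in this study at time the Informed Consent process has been completed". Read literally, 9.2 would therefore place in the safety set someone who withdraws after consent and before any dressing.

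**3. The clock and the catheter.** Catheters can predate the study. SAP 6.2.2 has a baseline variable that starts "Duration of tube insertion (days) = date of randomization" and counts back to insertion, and Protocol 10.2.2 re-dresses sites already in use. Protocol 10.2.4 records catheter duration and dressing duration separately, so either clock could be programmed. Example: a catheter inserted 20 h before the first study dressing and removed 6 h after it.
- From insertion: 20 + 6 = 26 h, in the safety set.
- From the first study dressing: 6 h, out.

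A catheter inserted at the time of the first dressing and removed at 20 h is out on both. For a catheter inserted no later than the first study dressing, the dressing clock excludes at least as many subjects as the insertion clock.

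SAP 6.3.1 notes that "some subject may have two or more than two CVC", and inclusion criterion IC-4 allows other deep vein catheters as well. The rule does not say whether one catheter above 24 hours is enough.

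**4. Illustrative size.** The documents give no share of subjects with short dwell. If 1%, 2% or 5% of 440 were affected (assumed), that would be 4.4, 8.8 or 22 subjects; it could also be none. For the effect on a rate, take an arm of 220 and an assumed serious adverse event rate of 10% (22/220), and exclude k subjects.

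| k | All had an event: (22 − k)/(220 − k) | Change (points) | None had an event: 22/(220 − k) | Change (points) |
|---|---|---|---|---|
| 1 | 21/219 = 9.59% | −0.41 | 22/219 = 10.05% | +0.05 |
| 2 | 20/218 = 9.17% | −0.83 | 22/218 = 10.09% | +0.09 |
| 5 | 17/215 = 7.91% | −2.09 | 22/215 = 10.23% | +0.23 |

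The shift can go either way. It is downward if the excluded subjects are mainly deaths.

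**The case against.** The case for leaving the text alone has real content. The wording refers to the catheter, which favors counting from insertion; on that clock a catheter already in for more than 24 hours at randomization qualifies at once, and the affected group shrinks. IC-2 expects an ICU stay of at least 3 days. SAP 6.4 plans listings of all adverse events, serious events and deaths, and SAP 6.2.1 lists non-completers. Suspected CLABSI/CRBSI is compared on the full analysis and per-protocol sets (SAP 6.3.2), with no 24-hour filter, and Protocol 19.4 plans an analysis of the number of deaths without tying it to the safety set. The sentence in Protocol 9.2 is awkwardly worded and may be meant only to say which set an early exit goes to.

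All of this limits the effect. It does not remove the mismatch: listings do not correct the numerators and denominators of tables, and no passage says whether 9.2 or 19.3 prevails.

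A reader might infer more, in two ways. One is that every exit in the first 24 hours of the study drops out of the safety set. The documents do not support this, because the rule concerns catheter dwell and not study time, and loss to follow-up means leaving with the CVC in place. The other is that early deaths will in fact disappear from the safety report. No count is given, the number may be zero, and the events should still appear in the listings.

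**Conclusion.** The concern holds in conditional form. As written, the safety set can exclude exposed subjects with a dwell of 24 hours or less from the safety tables. It conflicts with Protocol 9.2 for those among them who withdrew or discontinued (including deaths, if the exit list is read that way), and it cannot be programmed in only one way. The text mismatch is certain; the size is not. The effect is probably small and may be nil: a single excluded subject would move an assumed 10% rate in an arm of 220 by less than half a point. The 10% rate, the numbers excluded and the 1% to 5% shares are all assumptions, and no difference between the groups has been shown. The primary endpoint and power are not touched. The passages should be reconciled before the database is locked.

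**What to change.** - **Protocol 19.3 and SAP 5.3:** define the safety set as all randomized subjects with at least one study dressing applied, with no minimum dwell. State whether subjects are grouped by dressing received or as randomized; a rule is needed because SAP 6.2.1 foresees subjects who do not use the product as randomized.
- **Protocol 9.2:** say that subjects who withdraw or discontinue are in the safety set if at least one study dressing was applied. This also removes the consented but never dressed subject.
- **Any subset above 24 hours:** keep it only as a supplementary table, stating which catheter counts and whether time runs from insertion or from the first study dressing.

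The cost is one sentence in each of Protocol 19.3 and SAP 5.3 and one clause in Protocol 9.2. The protocol edits need ethics and regulatory approval as required (Protocol 21.0). Protocol 19.7 allows a change of analysis method before lock to be documented in the SAP. No new data are needed, since adverse events are already scheduled from Day 0 and at the withdrawal visit (Protocol 10.3).

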19.4 Statistical Analyses

For patient baseline characteristics and demographic data, quantitative data will be analyzed based on t-test or rank sum test, and qualitative information will be analyzed based on Chi-square test or Fisher's exact test. CVC tip bacterial colonization rates, PICCO/hemodialysis catheter bacterial colonization rates, catheter-related bloodstream infection rates, and microbial species analysis will be analyzed by chi-square test or Fisher's exact test. Other results collected in this study, such as wearing duration, frequency of replacement, skin condition, and number of deaths, will be analyzed using t-tests or rank sum tests accordingly. The O'Brien-Fleming expenditure function will be used twice in succession to determine the test boundaries.

In addition, descriptive summaries of effectiveness and safety evaluation indicators will be presented for the entire trial and for subjects in each group. For continuous data, the data will be summarized by number of subjects, mean, standard deviation (SD), median, minimum and maximum values. For categorical data, they will be summarized by frequency and corresponding percentage.

19.5 Planned Interim Analyses and Criteria for Clinical Investigation

Interim analysis will be conducted at enrollment to 220 subjects, and the total CVC tip colonization rate obtained from the interim analysis will be used to recalculate and evaluate the sample size.

19.6 Procedures for Missing, Unused or Spurious Data

Data for the validity evaluation indicator and safety evaluation indicator will not be interpolated. The interpolation of incomplete data will be further described in SAP.

Unused or erroneous data in the database will be identified and processed during the data management process.

19.7 Procedures for Reporting Deviations from Statistical Plan

If the method of analysis in this protocol changes before the data is locked, it will be documented in SAP. If there are changes to the analyses in the final SAP after data locking, they should be documented in the Statistical Analysis Report (SAR) and the Clinical Study Report (CSR).

19.8 Validation Plan

Independent validation of statistical plans and outputs will not be performed, and standard validation methods should be used (self-review of codes and logs, consistency review with other data sets and within the report, etc.).

20.0 CONFLICT OF INTEREST

The independence of this study from any actual or perceived influence, such as by the medical device industry, is critical. Therefore, any actual conflict of interest of persons who have a role in the design, conduct, analysis, publication, or any aspect of this trial will be disclosed and managed. Furthermore, persons who have a perceived conflict of interest will be required to have such conflicts managed in a way that is appropriate to their participation in the design and conduct of this trial. The Sponsor has established procedures for all Investigators to

disclose all conflicts of interest and will establish a mechanism for the management of all reported dualities of interest.

21.0 CLINICAL INVESTIGATION PLAN MODIFICATIONS

Modifications to this CIP may be necessary to protect the safety of the subjects and integrity of the data. In collaboration with the Investigator(s), modifications will be documented and submitted for ethical and regulatory approval (as required) prior to implementation. All changes will be evaluated for impact per Sponsor standard operating procedures (SOPs). Modifications will be considered implemented after all ethical and regulatory approvals (as required) are received and all key Sponsor and site staff has been trained.

22.0 PERIODIC REVIEWS

Ongoing reviews by IRB/EC are required for the duration of the clinical study. The Investigator will comply with local IRB/EC requirements for ongoing reviews, at a minimum annually. The Sponsor will provide an annual study report to participating Investigators.

23.0 INSURANCE

The Sponsor shall provide clinical study related insurance covering the reasonable, and necessary costs of diagnostic, therapeutic and medical treatment including hospitalization costs (treatment costs) for such participant injuries following the administration or use of the study device(s) in accordance with this clinical investigational plan and in accordance with the national regulations. The Sponsor may reimburse the institution and/or study participants for treatment costs depending on who incurred such treatment costs. The Sponsor will not be responsible for paying for or reimbursing treatment costs if (i) the injury is attributable to the negligence or misconduct of any agent or employee of the institution or Investigator, or the failure of such persons to comply with a study protocol, (ii) the treatment costs are covered by the study participant's medical or hospital insurance coverage, or (iii) the treatment costs arose as a result of the treatment of normal progression of the study participant's disease or

injuries resulting from interventions that the study participants would have incurred had they not participated in the study.

24.0 PUBLIC REGISTRATION AND PUBLICATION

The Sponsor shall ensure that this study will comply with any required national registration requirements. This study will be conducted in accordance with the applicable publication and data sharing policies and regulations.

26.0 GLOSSARY

| Abbreviations | Definitions |
|---------------|--|
| ADE | Adverse Device Effect |
| AE | Adverse Events |
| CHG | Chlorhexidine Gluconate |
| CLABSI | Central Line Associated Bloodstream Infections |
| CRA | Clinical Research Associate |
| CRO | Contract Research Organization |
| CRBSI | Catheter Related Blood Stream Infections |
| CVC | Central Venous Catheter |
| DVC | Deep Venous Catheters |
| eCRF | electronic Case Report Form |
| EC | Ethics Committee |
| EDC | Electronic Data Capture |
| FAS | Full Analysis Set |
| FDA | Food and Drug Administration |
| GCP | Good Clinical Practice |
| ICF | Informed Consent Form |
| IFU | Instruction for Use |
| NMPA | National Medical Products Administration |
| PD | Protocol Deviation |
| PI | Principal Investigator |
| PICCO | Pulse Index Continuous Cardiac Output |

| | |
|------|-------------------------------|
| PPS | Per Protocol Set |
| RBC | Red Blood Cell |
| SADE | Serious Adverse Device Effect |
| SAE | Serious Adverse Events |
| SAP | Statistical Analysis Plan |
| SAS | Statistical Analysis System |
| SD | Standard Deviation |
| SMV | Site Monitoring Visit |
| SOP | Standard Operating Procedure |
| SS | Safety Analysis Set |
| WBC | White Blood Cell |

